10.1.3 Unexpected Adverse Reaction

An unexpected adverse reaction is an adverse reaction, the nature and severity of which is not consistent with the applicable diet information.

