10 SAFETY INSTRUCTIONS AND GUIDANCE

10.1 Adverse Events and Laboratory Abnormalities

10.1.1 Adverse Events

An adverse event (AE) is any untoward medical occurrence in a clinical investigation participant who has been administered an investigational diet and does not necessarily have a causal relationship with this treatment. An AE can be any unfavorable and unintended sign (including an abnormal laboratory finding), symptom, or disease temporally associated with the use of a diet, whether or not it is considered related to that diet. Pre-existing conditions that worsen during a study are to be reported as AEs.

During the study, participants should record any adverse effects in their diary. At each visit the participant will be asked, "Have you experienced any difficulties or problems since I saw you last?". Any adverse events (AEs) will be documented in the study record and will be classified according to the description, duration, intensity, frequency, and outcome. The qualified investigator will assess any AEs and decide causality.

Intensity of AEs will be graded on a three-point scale (mild, moderate, severe) and reported in detail in the study record.

Mild:	Awareness of event but easily tolerated
Moderate:	Discomfort enough to cause some interference with usual activity
Severe:	Inability to carry out usual activity

The causality relationship of investigational diet to the adverse event will be assessed by the qualified investigator as either:

Most probable:	There is a reasonable relationship between the investigational diet and AEs. The event responds to withdrawal of investigational diet (dechallenge) and recurs with rechallenge when clinically feasible.
Probable:	There is a reasonable relationship between the investigational diet and AEs. The event responds to dechallenge.
Possible:	There is a reasonable relationship between the investigational diet and AEs. Dechallenge information is lacking or unclear.
Unlikely:	There is a temporal relationship to the investigational diet administration but there is no reasonable causal relationship between the investigational diet and the AEs.
Not related:	There is no temporal relationship to investigational diet administration or there is a reasonable causal relationship between non-investigational diet, concurrent disease or circumstance and the AEs.

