10.1.2 Serious Adverse Event

A serious adverse event (SAE) is any experience that suggests a significant hazard, contraindication, side effect or precaution. It is any AE that results in any of the following outcomes:

1. Death
2. A life-threatening adverse event
3. Inpatient hospitalization or prolongation of existing hospitalization
4. A persistent or significant disability or incapacity
5. A congenital anomaly/birth defect in the offspring of a participant who received the study treatment

Important medical events that may not be immediately life-threatening or result in death or hospitalization but may jeopardize the participant or may require intervention to prevent one of the outcomes listed above. Examples of such events are intensive treatment in an emergency room or at home for allergic bronchospasm; blood dyscrasias or convulsions that do not result in hospitalization; or the development of drug dependency or drug abuse.

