10.3 Reporting of SAEs And Unexpected Adverse Reactions

The qualified investigator will be responsible for classification of an AE as an SAE within 24 hours of notification. Causality should be signed off by the qualified investigator prior to reporting to ethics and regulatory bodies. Notification of any serious adverse events must be made in writing to the study sponsor. The IRB will be notified of all diet related SAEs and unexpected adverse reactions. All blinded SAE's or unblinded-participant-on-active product SAE's will be reported to the Therapeutics Products Directorate (TPD) in an expedited manner.

KGK Science must notify the TPD of all blinded or unblinded-participant-on-active product serious adverse events and reactions as follows:

If it is neither fatal or life threatening, within 15 calendar days after the day on which the sponsor becomes aware of the information; and

If it is fatal or life threatening, must be reported as soon as possible, but not later than seven (7) days after the day on which the sponsor becomes aware of the information.

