11 STATISTICAL EVALUATION

11.1 Determination of Sample Size

Because this is a pilot study to explore the efficacy and safety of Nic's Ketogenic Diet, sample size will not be calculated. A total of 14 participants will be enrolled.

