13.1 IRB Approval

KGK Science Inc. will supply relevant documents for submission to an IRB for the protocol's review and approval. The following must be submitted to the IRB: this protocol, a copy of the informed consent form, and, if applicable, volunteer recruitment materials and/or advertisements and other documents required by all applicable laws and regulations. The IRB's written approval of the protocol and volunteer informed consent must be obtained before commencement of the study. The IRB approval must refer to the study by exact protocol title, number, and version date; identify versions of other documents (e.g., informed consent form) reviewed; and state the approval date.

KGK must adhere to all requirements stipulated by the IRB. This may include notification to the IRB regarding protocol amendments, updates to the informed consent form, recruitment materials intended for viewing by volunteers, local safety reporting requirements and submission of the investigator's annual/final status report to the IRB.

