13.3 Potential Risks and Procedures to Minimize Risk

All potential risks are disclosed to study participants prior to their participation. The potential risks associated with this study include those associated with venipuncture and switching from a carbohydrate-rich diet to a ketogenic diet. Risks associated with venipuncture include pain, bruising, and infection at the site. Alcohol swabs and proper venipuncture procedure will be followed to minimize the risk of infection. The potential short-term side effects of the ketogenic diet are nausea, vomiting, headache, fatigue, dizziness, insomnia, and constipation.

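### Section 10.1.3 ties an unexpected reaction to a mismatch in nature *and* severity, so some non-serious reactions can fall outside the IRB notification that Section 10.3 requires

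*Combined protocol and SAP*

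**What the plan says.** Section 10.1.3 defines an unexpected adverse reaction in one sentence, as a reaction "the nature and severity of which is not consistent with the applicable diet information". No other section restates the definition, and none says which document holds the diet information.

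Section 10.3 puts the definition to use: "The IRB will be notified of all diet related SAEs and unexpected adverse reactions". That gives two triggers for the IRB: a diet-related SAE, and an unexpected reaction. The other notices in Section 10.3, to the sponsor and to the regulator, concern serious events.

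Section 13.3 names the anticipated effects: "The potential short-term side effects of the ketogenic diet are nausea, vomiting, headache, fatigue, dizziness, insomnia, and constipation". That is seven effects by name, with no intensity attached to any of them.

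Intensity and seriousness are separate scales. Section 10.1.1 describes a severe event as "Inability to carry out usual activity". Section 10.1.2 defines an SAE by outcome, for example "Inpatient hospitalization or prolongation of existing hospitalization", and adds important medical events that "may jeopardize the participant or may require intervention to prevent one of the outcomes listed above".

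**The concern.** Expectedness has two parts: what kind of reaction it is, and how bad it is. A definition joined by *and* asks for a mismatch on both. A symptom that is on the list matches in kind, so on the literal reading it cannot be unexpected however intense it becomes. By the same logic, a reaction that is not on the list but is of ordinary severity mismatches on one part only.

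For non-serious reactions this definition decides what the IRB must be told. The seven symptoms in Section 13.3 are the harms that the protocol itself anticipates over 140 days on the diet, and Section 11.1 gives exploring safety as one purpose of the pilot. A worse-than-anticipated form of one of those symptoms is something an IRB would reasonably want to hear about while participants are still on the diet. Under the literal wording the site could follow the protocol exactly and not send that notice. Under a looser reading it would send it. Two people applying the same sentence could act differently on the same event.

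**Working it through.** No figure in the plan bears on this point and there is no calculation to reproduce; Section 11.1 states that "sample size will not be calculated". The check sets the definition in 10.1.3 against the reporting rule in 10.3, the intensity scale in 10.1.1, the SAE definition in 10.1.2 and the list in 13.3.

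Step 1: sort diet-related reactions by kind (listed or not) and by severity (as expected or not), and ask whether Section 10.3 requires IRB notice.

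| Kind | Severity | Non-serious, *and* read literally | Non-serious, with *or* | Diet-related SAE, either wording |
|---|---|---|---|---|
| Listed | As expected | No | No | Yes |
| Listed | Greater than expected | **No** | Yes | Yes |
| Not listed | Unremarkable | **No** | Yes | Yes |
| Not listed | Also inconsistent | Yes | Yes | Yes |

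The two bold cells are the gap. The last column does not depend on the definition, because Section 10.3 notifies diet-related SAEs without asking whether they were expected.

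Step 2: check that the second row can occur. Vomiting that stops a participant's usual activities is severe under 10.1.1. If it leads to none of the five numbered outcomes in 10.1.2 and is not an important medical event, it is not an SAE. It is on the list in 13.3, so it is consistent in kind. Neither trigger in 10.3 then applies.

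Step 3: check whether severity can be compared at all. Section 13.3 gives none. Section 9.7.7 mentions other things that participants are told to expect from the diet, also without severities. The e-book, its summary and the consent form may say more, but they are not part of the documents reviewed here, and 10.1.3 does not point to any of them.

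Step 4: scale. The documents give no expected number of severe, non-serious, diet-related reactions, so no rate can be derived. For scale only: one such participant would be 1/14 = 7.1% of the sample and two would be 2/14 = 14.3%. These are not predictions.

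**The case against.** A reader might infer that a listed side effect far worse than expected never has to reach the IRB. The documents do not support that. Once such an effect is serious and judged related to the diet, Section 10.3 requires notice whatever its expectedness, and the important-medical-event text in 10.1.2 makes the serious category broad. The worst cases are covered.

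A reader might also infer that the study would lose sight of a severity signal. It would not. Section 10.1.1 has every event graded for intensity, Section 10.2.1 has events followed up until they resolve or stabilize, and Section 11.3.2 reports intensity, relationship and outcome for each event. What is affected is notification to the IRB, not data capture or analysis.

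Three further arguments have some force.

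- The sentence can be read as saying that the reaction's overall profile does not match, in which case a mismatch in severity alone would qualify. That is a possible reading, so the text is ambiguous rather than plainly exclusionary. The ambiguity calls for the same edit.
- For an unlisted reaction, one could say that no stated severity exists for it to be consistent with, so it fails on both counts. This makes the unlisted half of the gap more dependent on interpretation than the listed half. With *or* the question does not arise.
- Section 13.1 binds the site to whatever the IRB stipulates, which may include "local safety reporting requirements". Such a requirement could catch some of these reactions, so it would be wrong to say that they have no possible route. It is conditional, however, and lies outside the protocol's own rule.

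Finally, changing *and* to *or* achieves little on severity if there is nothing to compare it with. That is correct, and it is why the fix also asks for a named reference.

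**Conclusion.** The point holds in a limited form. On its literal reading, Section 10.1.3 leaves two kinds of non-serious reaction outside the unexpected category, and so outside the only IRB trigger that Section 10.3 gives for non-serious reactions: a listed effect that is worse than expected, and an unlisted effect of unremarkable severity. On the looser reading the definition is unclear about whether one mismatch is enough. Nothing elsewhere in the protocol settles it.

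The size is modest. The gap concerns IRB notification of non-serious reactions only. Notification of diet-related SAEs, the grading and reporting of all adverse events, and the efficacy analysis are unaffected. How many reactions would fall into the gap cannot be estimated from the documents. The conclusion assumes that no IRB stipulation or unseen diet document already supplies a clearer rule. It is worth correcting because the sentence governs safety reporting and the correction is nearly free.

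**What to change.** In Section 10.1.3, change *nature and severity* to *nature or severity*, so that a mismatch in either is enough.

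In the same section, name the document that serves as the diet information. If it is Section 13.3, that list carries no severities, so the sponsor should make sure that the named reference lets severity be assessed. The documents offer no basis for assigning an expected intensity to each of the seven effects, so how this is done should be left to the sponsor.

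The cost is one word and one short addition to the protocol, some work for the sponsor if the chosen reference is silent on severity, and possibly a few more IRB notices. Visits, data collection, sample size and statistical analysis do not change.

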10.1.4 Laboratory Test Abnormalities

The investigator must assess the clinical significance of all abnormal laboratory values as defined by the compendium of normal values for the reference laboratory.

Any treatment emergent abnormal laboratory result which is clinically significant, i.e., meeting one or more of the following conditions, should be recorded as a single diagnosis on the AEs form in the study record:

1. Accompanied by clinical symptoms
2. Leading to interruption or discontinuation of the investigational diet
3. Requiring a change in concomitant therapy

This applies to any protocol and non-protocol specified laboratory result from tests performed after the first day of the investigational diet, which falls outside the laboratory reference range and meets the clinical significance criteria for liver and kidney tests as well as for hematology and clinical chemistry, etc. (i.e. AST and/or ALT > 2 x ULN).

This does not apply to any abnormal laboratory result which falls outside the laboratory reference range but which does not meet the clinical significance criteria or those which are a result of an AE which has already been reported.

Any laboratory result abnormality fulfilling the criteria for a serious adverse event (SAE) should be reported as such, in addition to being reported as an AE in the study record.

10.2 Treatment and Follow-Up of AEs And Laboratory Abnormalities

10.2.1 Treatment and Follow-up of AEs

AEs, especially those for which the relationship to the investigational diet is suspected, should be followed up until they have returned to baseline status or stabilized.

If after follow-up, return to baseline status or stabilization cannot be established, an explanation should be recorded in the study record.

10.2.2 Treatment and Follow-up of Laboratory Abnormalities

In the event of participant-initiated withdrawal or clinically significant unexplained abnormal laboratory test values, the participant will be withdrawn from the treatment and will remain in the study and be required to attend all remaining study visits as part of a safety arm.

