1.3 Schedule of Assessments

Procedures	Visit 1 Screening	Visit 2 Day 0 (Baseline)	Visit 3–7 Day 28–112 Week 4–16	Visit 8 Day 140 Week 20
Informed consent	X			
Review inclusion/exclusion criteria	X	X		
Review medical history	X			
Review concomitant therapies	X	X	X	X
Vitals: Height*, weight, heart rate, blood pressure *Height will only be measured at visit 1	X	X	X	X
Urine pregnancy test	X	X		X
Physical examination		X		
Blood collection for analysis of: CBC, electrolytes (Na ⁺ , K ⁺ , Cl ⁻ , P), HbA1c, fasting glucose, eGFR, creatinine, AST, ALT, total bilirubin, and TSH *TSH will only be measured at visit 1	X			X
DEXA scan** **DEXA will be measured at Visits, 2, 5 and 8 only		X	X	X
ECG** **ECG will be measured at Visits, 2, 5 and 8 only		X	X	X
Blood Markers: Fasting glucose, HbA1c, C-reactive protein, lipid panel, Free Tri-iodothyronine (T3), ESR		X		X
Lipid Panel	X		X	
Nutritional Counselling [#] and dispense Nic’s Keto Diet e-book #As required, remote Nutritional Counselling will be completed on 3-day food records weekly throughout study period		X		
Daily glucose monitors, and keto monitors Dispensed		X	X	
Daily glucose monitors, and keto monitors Returned			X	X
Food Records Dispensed	X	X	X	
Food Records Returned		X	X	X
Subject Diary Dispensed		X	X	
Subject Diary Returned			X	X
Compliance Calculated			X	X
Adverse Events	X	X	X	X

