9.4 Visit 5 (Day 70 ± 3 days)

Participants will return to the clinic after a 12-hour fast to complete assessments for Visit 5 with completed food records and subject treatment diary.

Assessments for Visits 5 include:

1. Collection and review of subject treatment diary
2. Collection and review of food records
3. Compliance calculation
4. Review of concomitant therapies and adverse events
5. Collection of fasted ketone and glucose and review of glucose and ketone monitors
6. Seated resting blood pressure and heart rate measurements
7. Weight measurement and BMI calculation (Section 9.5.1)
8. Total body DEXA scan and ECG
9. Collection of blood sample for lipid panel analysis (Section 9.5.2)
10. Dispense or assign dates of 3-day food records
11. Re-dispense subject treatment diary

The next visit will be scheduled for day 84

Reminders for participants prior to their next in-clinic visit:

1. Return to the clinic in a 12-hour fasted state
2. Complete 3-day food records weekly. Weekly records will be reviewed by nutrition team and counselling provided as required.
3. Abide by instructions for medications as per Section 7.3.1 and OTC medications, supplements, and food and drinks as per Section 7.3.2.
4. Complete subject treatment diary
5. Maintain similar physical activity and study diet
6. Monitor glucose and ketones daily

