9.7.5 Dual Energy X-Ray Absorptiometry (DEXA) Scan

The DEXA scan will be performed at the KGK clinic (London, ON) or a local facility at visits 2 (Day 0), visit 5 (Day 84), and visit 7 (Day 140) by trained technicians. The DEXA scan is a form of X-ray radiation that measures the body tissue density which will be converted and used for assessment of the study outcomes. Coordinators will remind participants 24 hours before the day of the DEXA assessment for the necessary instructions prior to the scan.

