9.9 Laboratory Analyses

Blood samples will be drawn from the participants at screening (Visit 1), baseline (Visit 2, Day 0), Visit 3, Visit 4, Visit 5, Visit 6, Visit 7, and at the End of Study visit (Visit 8, day 140) as indicated in the schedule of assessments.

Protection of subject confidentiality will extend to all data generated from the assaying of these samples. These samples will be alphanumerically coded and the persons performing the analysis will not be aware of the subject's identity.

At screening (Visit 1), 13 mL of ≥ 12 hours fasted whole blood will be collected in:

1. Two 4mL EDTA vacutainer tubes to generate plasma for:
 - a. CBC analysis (one tube)
 - b. Hb1Ac analysis (one tube)

2. One 5mL SST vacutainer tube to generate serum for:
 - a. Electrolytes (Na⁺, K⁺, Cl⁻, P), lipid profile, fasting glucose, eGFR, creatinine, AST, ALT, TSH, and total bilirubin

At baseline (Visit 2), 13 mL of ≥ 12 hour fasted whole blood will be collected in:

1. Two 4mL EDTA vacutainer tubes to generate plasma for:
 - a. Hb1-Ac (one tube)
 - b. ESR (One Tube)
2. One 5mL SST vacutainer tube to generate serum for:
 - a. Fasting glucose, C-reactive protein, lipid panel, Free T3 (one tube)

At Visit 3, 5 mL of ≥ 12 hour fasted whole blood will be collected in:

1. One 5mL SST vacutainer tube to generate serum for:
 - a. Lipid Panel (one tube)

At Visit 4, 5 mL of ≥ 12 hour fasted whole blood will be collected in:

1. One 5mL SST vacutainer tube to generate serum for:
 - a. Lipid Panel (one tube)

At Visit 5, 5 mL of ≥ 12 hour fasted whole blood will be collected in:

1. One 5mL SST vacutainer tube to generate serum for:
 - a. Lipid Panel (one tube)

At Visit 6, 5 mL of ≥ 12 hour fasted whole blood will be collected in:

1. One 5mL SST vacutainer tube to generate serum for:
 - a. Lipid Panel (one tube)

At Visit 7, 5 mL of ≥ 12 hour fasted whole blood will be collected in:

1. One 5mL SST vacutainer tube to generate serum for:
 - a. Lipid Panel (one tube)

At the end of the study (Visit 8), 17 mL ≥ 12 hour fasted whole blood will be collected in:

1. Three 4mL EDTA vacutainer tubes to generate plasma for:
 - a. CBC analysis (one tube)
 - b. Hb1Ac analysis (one tube)

c. ESR (One Tube)

2. One 5mL SST vacutainer tube to generate serum for:
 - a. Electrolytes (Na⁺, K⁺, Cl⁻, P), fasting glucose, eGFR, creatinine, AST, ALT, CRP, Lipid Panel, Free T3, and total bilirubin (one tube)

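### No blood count, electrolyte, kidney or liver test is scheduled on the diet before Day 140, and Visit 5 is the only DEXA visit without a pregnancy test

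*Combined protocol and SAP*

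**What the plan says.** **The rules.** Section 10.2.2 says that, for "clinically significant unexplained abnormal laboratory test values, the participant will be withdrawn from the treatment and will remain in the study", with attendance at the remaining visits as a safety arm. Section 10.1.4 sets when an abnormal result is recorded as an adverse event. It covers "any protocol and non-protocol specified laboratory result from tests performed after the first day of the investigational diet" that falls outside the reference range and "meets the clinical significance criteria for liver and kidney tests as well as for hematology and clinical chemistry", and gives AST and/or ALT above twice the upper limit of normal as its example. Section 7.4 withdraws any participant who becomes pregnant.

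**The schedule.** In Section 1.3 the row beginning "Blood collection for analysis of: CBC, electrolytes" is marked at Visit 1 and Visit 8 only. Sections 9.1 to 9.6 and the tube list in 9.9 agree: Visits 3 to 7 each draw one 5 mL SST tube, for a lipid panel.

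**The scans.** A footnote in 1.3 states "DEXA will be measured at Visits, 2, 5 and 8 only", and the Visit 5 list in 9.4 includes "Total body DEXA scan and ECG". Urine pregnancy tests are marked at Visits 1, 2 and 8. Section 9.7.5 describes DEXA as X-ray radiation but labels the later scans "visit 5 (Day 84), and visit 7 (Day 140) by trained technicians", which does not match 1.3, 9.4 or 9.6.

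**The concern.** A rule that stops the diet on a laboratory result needs results while the diet is running. For the liver, kidney, hematology and chemistry tests that 10.1.4 refers to, the only scheduled on-diet result arrives at the last visit. By then there is no diet to stop and no remaining visit for a safety arm to attend.

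Before Visit 8 the rule can act on these tests in three ways: an unscheduled sample (9.9), a result obtained outside the protocol (10.1.4), or end-of-treatment evaluations done where possible at early withdrawal (7.4). None of these is prompted by a symptom-free change in someone who stays on the diet.

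The pregnancy point is separate but has the same cause, since the Visit 5 procedures were set without a matching safety check. An unrecognised pregnancy could be exposed to the Visit 5 scan and continue on the diet until Visit 8.

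Participant safety is what is at stake. The inflammation endpoints are not.

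**Working it through.** **1. Is the tube list complete?** The plan's own figure is about 68 mL in total (9.9). From the tube lists:

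- Visit 1: 2 × 4 + 5 = 13 mL
- Visit 2: 2 × 4 + 5 = 13 mL
- Visits 3 to 7: 5 × 5 = 25 mL
- Visit 8: 3 × 4 + 5 = 17 mL
- Total: 13 + 13 + 25 + 17 = 68 mL

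The stated total is reproduced, so no safety draw is hidden at Visits 3 to 7.

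**2. What is tested when** (1.3, 9.1 to 9.6, 9.9):

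| Visit | Day | CBC, electrolytes, kidney, liver | DEXA | Pregnancy test |
|---|---|---|---|---|
| 1 | −45 to −1 | yes | no | yes |
| 2 | 0 | no | yes | yes |
| 3, 4 | 28, 56 | no (lipids only) | no | no |
| 5 | 70 | no (lipids only) | yes | no |
| 6, 7 | 84, 112 | no (lipids only) | no | no |
| 8 | 140 | yes | yes | yes |

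Of the six on-diet draws (Visits 3 to 8), the first five carry none of these tests. DEXA visits {2, 5, 8} minus pregnancy-test visits {1, 2, 8} leaves {5}.

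The visit 7 label in 9.7.5 is attached to Day 140, which is Visit 8 everywhere else, so I read it as a labelling error. Taken literally, it would add a second scan visit without a test.

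**3. Gaps as planned** (windows of ±3 days at Visits 5 and 8):

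- Diet start to first on-diet panel: 140 ± 3 = 137 to 143 days.
- Panel to panel, Visit 1 to Visit 8: 137 + 1 = 138 to 143 + 45 = 188 days.
- Last scheduled pregnancy test (Day 0) to the Visit 5 scan: 70 ± 3 = 67 to 73 days under 9.4. Under 9.7.5 it is 84 days, or 81 to 87 if the same window is assumed. Either date lies in the untested interval.

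**4. Gaps with chemistry added at Visit 5:**

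- Diet start to Visit 5: 67 to 73 days.
- Visit 5 to Visit 8: 137 − 73 = 64 to 143 − 67 = 76 days, so the longest on-diet gap is at most 76 days.
- Panel to panel, Visit 1 to Visit 5: 67 + 1 = 68 to 73 + 45 = 118 days.
- Diet time left for 10.2.2 to act after a Visit 5 draw: 140 − 70 = 70 days, less laboratory turnaround, and three visits (6, 7, 8). After Visit 8 both figures are 0.

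**5. Is it feasible on the existing blood?** At Visit 1 one 5 mL SST tube carries electrolytes together with "lipid profile, fasting glucose, eGFR, creatinine, AST, ALT, TSH, and total bilirubin". At Visit 8 one such tube again carries this chemistry plus lipids. Running the chemistry on the Visit 5 lipid tube therefore adds 0 mL and the total stays at 68 mL. An optional CBC at Visit 5 adds one 4 mL EDTA tube: 68 + 4 = 72 mL in total and 5 + 4 = 9 mL at that draw, against the 18 mL per-visit figure in 9.9.

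**The case against.** The strongest reply is that how often to run safety chemistry in a 14-person healthy-volunteer pilot is a matter of judgement. Section 5 promises these analytes as safety outcomes without an interim time point, and a before-and-after measurement delivers that. The diet risks listed in 13.3 are symptoms, and adverse events are asked about at every visit. The documents give no rate of laboratory change and no DEXA dose, so the sizes above are calendar intervals, not measures of harm. All of this stands, and it limits how strongly the point can be put.

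Other parts stand in part:

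- **10.2.2 is a general rule.** It can still be triggered by the lipid panels and arguably by glucose readings. Meter glucose and ketones, vitals and the Visit 5 ECG also continue. None of these measures the missing tests or detects a pregnancy.
- **10.1.4 ties clinical significance to symptoms, interruption of the diet or a change in concomitant therapy.** A silent change would therefore need an investigator's decision to qualify, although the AST/ALT example points the other way. In either case the investigator needs a result to decide on.
- **10.2.1 requires adverse events to be followed until they resolve or stabilise.** An abnormality found at Visit 8 that qualifies as an adverse event would be followed, and the study diet ends then anyway. That limits later harm but does not shorten the exposure.
- **Pregnancy is made unlikely** by required contraception, exclusion of women planning pregnancy and two tests before the diet. The number of women is not given and could be zero. This lowers the risk but does not explain why Visit 5 differs from the other two scan visits.
- **In the Visit 8 list (9.6) the scan comes before the pregnancy test.** The numbered lists do not state a mandatory order, but fixing the order there is a sensible addition.

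**Conclusion.** The point holds, with high confidence on the facts: the schedule, visit lists and tube list agree with one another, and the blood volume reproduces. For CBC, electrolytes, kidney and liver tests, the diet-stopping rule has no scheduled input for 137 to 143 days of diet, and pregnancy tests cover only two of the three DEXA visits.

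This rests on reading Visit 5 as Day 70 and the Day 140 scan as Visit 8, as 1.3, 9.4 and 9.6 have them, and on the plan being followed without unscheduled samples. The clinical risk cannot be quantified from the documents and is lowered by the eligibility criteria, including exclusion for clinically significant abnormal screening results. The study is not invalidated. This is an inexpensive safety improvement that the sponsor should make.

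**What to change.** Amend Sections 1.3, 9.4 and 9.9:

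1. At Visit 5, run electrolytes, creatinine/eGFR, AST, ALT and total bilirubin on the 5 mL SST tube already drawn for lipids.
2. At Visit 5, require a negative urine pregnancy test before the DEXA scan for women of child-bearing potential.

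Suggested text: *At Visit 5, electrolytes, creatinine/eGFR, AST, ALT and total bilirubin will be measured on the serum tube drawn for the lipid panel. Women of child-bearing potential must have a negative urine pregnancy test before the Visit 5 DEXA scan.*

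In the same amendment, correct the visit and day labels in 9.7.5 and state in 9.6 that the pregnancy test precedes the Visit 8 scan.

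Optional, at the sponsor's judgement:

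- CBC at Visit 5. Blood counts stay unmonitored on the diet unless this is taken.
- The same chemistry at Visit 3. This brings the first check forward to about Day 28, though the longest gap (Visit 5 to Visit 8) stays at up to 76 days.

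**Cost.** The recommended part needs one protocol amendment, 14 chemistry panels (one per participant) and 0 to 14 urine kits, with no extra visit, needle, tube or blood volume. The optional CBC adds one 4 mL EDTA tube per participant, and the optional Visit 3 chemistry adds 14 panels. The downside is modest assay and kit cost and some incidental results for the investigator to review.
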